### **7.4 Analysis Populations**

The following populations will be analyzed for overall treatment group (JBPOS0101):

- All Enrolled Population: The Enrolled Population will include all patients who signed informed consent.
- Safety Population: The safety population will include all patients who were treated with at least one dose of the investigational product. The safety population will be used for all safety assessments.
- Efficacy Population (EAS): The efficacy population will include all patients, without any major protocol deviation affecting the efficacy endpoint analysis, who were treated with the investigational product for at least 26 days and completed the Day 28 (Visit 5 [ $\pm$  2 days]) overnight video-EEG. The EAS will be used for all efficacy assessments.
- Modified Efficacy Population (mEAS): To evaluate the influence of COVID-19 on the efficacy results, a modified EAS will be considered which, in addition to EAS population, includes also those patients with major protocol deviations affecting the efficacy endpoint analysis which can be attributed to COVID-19. The same efficacy analyses as for EAS population will also be performed for the mEAS population.
- PK Population: The PK population will include all patients, without any major protocol deviation affecting the secondary endpoint analysis, who were treated with at least one dose of the investigational product and have at least one measurable PK concentration. The PK Population will be used for all PK assessments.

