4.2.2 Handling of Withdrawals

Patients are free to withdraw from the study or study treatment at any time upon request. Patient participation in the study may be stopped at any time at the discretion of the investigator or at the request of the sponsor.

At the discretion of the investigator, patients who withdraw from the study prematurely may receive tapered doses of investigational product before discontinuing. The tapering schedule for early withdrawal patients will be determined on a case-by-case basis and the medical monitor will be available for assistance if needed. When a patient withdraws from the study treatment or active participation in the study, the reason(s) for withdrawal shall be recorded by the investigator on the relevant page of the electronic case report form (eCRF).

If a patient discontinues the study prematurely, investigator's assessment of efficacy and tolerability of the investigational product will be recorded on Visit 6 (\pm 5 days).

Whenever possible, all patients who discontinue study treatment or withdraw from the study prematurely will undergo all end-of-study (Visit 6) assessments. Patients who fail to undergo final assessments will be contacted by the study site in an attempt to have them comply with the protocol. Following a minimum of 2 documented unsuccessful telephone calls, a registered letter will be sent to the patient in a final attempt to ensure protocol compliance.

It is vital to obtain follow-up data on any patient withdrawn because of an AE or SAE. In every case, efforts must be made to undertake protocol-specified safety follow-up procedures.

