7.5 Analysis Sets

The following analysis sets will be used in the statistical analyses.

Safety analysis set: The safety analysis set will include all patients who were treated with at least one dose of the investigational product. The safety analysis set will be used for all safety assessments.

Efficacy analysis set (EAS): The efficacy analysis set will include all patients, without any major protocol deviation affecting the efficacy endpoint analysis, who were treated with the investigational product for at least 26 days and completed the Day 28 (Visit 5 [\pm 2 days]) overnight video-EEG. The EAS will be used for all efficacy assessments.

Pharmacokinetic (PK) analysis set: The PK analysis set will include all patients, without any major protocol deviation affecting the secondary endpoint analysis, who were treated with at least one dose of the investigational product and have at least one measurable PK concentration. The PK analysis set will be used for all PK assessments.

Modified efficacy analysis set (mEAS): To evaluate the influence of COVID-19 on the efficacy results, a modified EAS will be considered which, in addition to the original EAS, includes also those patients with major protocol deviations affecting the efficacy endpoint analysis which can be attributed to COVID-19. The same efficacy analyses as in the EAS will also be performed for the mEAS. If both populations coincide (i.e., there are no major protocol violations attributable to COVID-19 which affect the efficacy endpoint analysis) only the analyses in the EAS will be performed.

Other additional listings due to COVID-19 may be described in the SAP.

The major protocol deviations leading to exclusion from the EAS and PK analysis set will be specified in the SAP and finalized prior to the database lock.

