13.1 Appendix: Schedule of Events

Table 13-1 Schedule of Events

Procedure	Screening Period	Treatment Period 1						Treatment Period 2: Dose Tapering Period	Follow-Up
		Visit 1	Visit 2	Telephone Contact	Visit 3	Telephone Contact	Visit 4		
Visit	Visit 1	Visit 2	Telephone Contact	Visit 3	Telephone Contact	Visit 4	Visit 5	Visit 6 / Early Termination Visit	Visit 7
Study Days	-28 to -6	1	2 to 6 ^a	7	12 or 13 or 14 ^a	21	28	42	56
Visit Window				± 2 days		± 2 days	± 2 days	± 5 days	± 5 days
Informed consent	X								
Medical history	X								
Inclusion/exclusion criteria	X								
Video EEG ^b	X						X		
BASED Score	X						X		
Demographics	X								
12-lead electrocardiogram	X			X			X	X	
Urine drug screen ^c	X								
Physical and neurological examination ^d	X	X	X ^e	X		X	X	X	X
Vital sign measurements ^f	X	X		X		X	X	X	X
Clinical laboratory tests ^g	X			X			X	X	
Investigational product administration ^h		X	X	X	X	X	X		

Procedure	Screening Period	Treatment Period 1						Treatment Period 2: Dose Tapering Period	Follow-Up
		Visit 1	Visit 2	Telephone Contact	Visit 3	Telephone Contact	Visit 4		
Visit	Visit 1	Visit 2	Telephone Contact	Visit 3	Telephone Contact	Visit 4	Visit 5	Visit 6 / Early Termination Visit	Visit 7
Study Days	-28 to -6	1	2 to 6 ^a	7	12 or 13 or 14 ^a	21	28	42	56
Visit Window				± 2 days		± 2 days	± 2 days	± 5 days	± 5 days
Dispensing of investigational product		X		X		X	X		
Investigational product accountability assessment				X		X	X	X	X
Adverse event monitoring		X	X	X	X	X	X	X	X
Review of prior and concomitant medications ^j	X	X	X	X		X	X	X	X
Clinical Global Impression of Change ^m		X		X		X	X	X	
Seizure diary ^j	X	X	X	X	X	X	X	X	
Pharmacokinetic blood sampling ^k		X				X			
Pharmacokinetic urine sampling ^l		X				X			

Abbreviations: EEG, electroencephalogram

- The investigator or his/her delegate will follow-up by telephone or email on Day 2 to Day 6 to ensure that the seizure diary is being completed, to review seizure counts, and to conduct daily assessments. The investigator will also contact the parent/caregiver by telephone on Day 12, or Day 13 or Day 14 to review seizure counts and to assess the patient's status.
- An overnight video-EEG will be completed within the Screening Period (Days -28 to -6), and repeated at Day 28 (Visit 5 [± 2 days]), [REDACTED]
[REDACTED]
- Urine drug screen assessment to test for the presence of cannabinoids will be performed locally.

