## 7 STATISTICAL METHODS

### 7.1 General

All statistical analysis will be conducted following the principles specified in the International Conference on Harmonization (ICH) Topic E9 Statistical Principles for Clinical Trials (CPMP/ICH/363/96).

All statistical analyses will be performed using the statistical software SAS, Version 9.4 or newer and any exceptions will be detailed in the CSR.

All results collected in the database will be presented in listings. Both absolute values and change-from-baseline values for each subject will be given where applicable. All continuous data will be listed with the same precision as presented in the database. Data listings will be sorted by subject ID, and time point.

Unless otherwise noted, continuous variables will be summarized using the number of non-missing observations (n), arithmetic mean (mean), standard deviation (SD), median, minimum, maximum, Quartile 1 (Q1), and Quartile 3 (Q3); categorical variables will be summarized using the frequency count and the percentage of subjects in each category. Time to event data will be summarized using median, 25%, and 75% percentiles.

In the data listings, study day relative to first dose of treatment may be presented. Study day relative to first dose will be calculated as: event date – first dose date (+1 if event date  $\geq$  first dose date).

Baseline will be the last non-missing available measurement prior to first dose of the study drug.

For safety summaries, the unscheduled and repeat assessments will not be summarized; however, all results will be included in the data listings.

All PK parameters will be summarized by the overall treatment group using descriptive statistics to include, as appropriate, n, mean, SD, coefficient of variation (CV), minimum, median, maximum, geometric mean (GM), and geometric CV.

Disposition, demographics and baseline characteristics, all safety parameters and adverse events will be summarized overall.

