### 7.2 Handling of Dropouts or Missing Data

Missing data will not be imputed.

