## 8 TABLES, FIGURES, AND LISTINGS

Table/Figure Number	Table/Figure Name
Section 14.1	Demographic and Subject Characteristics Data Summaries
Table 14.1.1	Summary of Subject Disposition (All Enrolled Population)
Table 14.1.2	Analysis Populations (All Enrolled Population)
Table 14.1.3	Summary of Demographic and Baseline Characteristics (Safety Population)
Table 14.1.4	Summary of Medical History (Safety Population)
Table 14.1.5	Summary of Prior & Concomitant Medications (Safety Population)
Table 14.1.6	Summary of Exposure (Safety Population)
Section 14.2	Pharmacokinetic and Efficacy Data Summaries
Table 14.2.1.1	Summary of Electroencephalogram Responses (EAS Population)
Table 14.2.1.2	Summary of Electroencephalogram Responses (mEAS Population)
Table 14.2.2.1	Descriptive Summary for Time to Relapse, Resolution of Spasms and Hypsarrhythmia during Dose Tapering Period (EAS Population)
Table 14.2.2.2	Descriptive Summary for Time to Relapse, Resolution of Spasms and Hypsarrhythmia during Dose Tapering Period (mEAS Population)
Table 14.2.3.1.1	Summary of Seizure Diary Card (EAS Population)
Table 14.2.3.1.2	Summary of Seizure Diary Card (mEAS Population)
Table 14.2.3.2.1	Summary of Seizure Diary Review (EAS Population)
Table 14.2.3.2.2	Summary of Seizure Diary Review (mEAS Population)
Table 14.2.4.1	Summary of CGI-C Assessments Results (EAS Population)

---

Table 14.2.4.2	Summary of CGI-C Assessments Results (mEAS Population)
Table 14.2.5	Summary of Pharmacokinetic Plasma JBPOS0101 Concentrations (PK population)
Table 14.2.6	Summary of Pharmacokinetic Urine JBPOS0101 Concentrations (PK population)
Table 14.2.7	Summary of Urine Volume (PK population)
Figure 14.2.1	Mean (+SD) Plasma JBPOS0101 Concentrations vs Time for Day 1 (PK Population) ( Note: Present in linear and semi-log scales. )
Figure 14.2.2	Mean (+SD) Plasma JBPOS0101 Concentrations vs Time for Day 21 (PK Population) ( Note: Present in linear and semi-log scales. )
Section 14.3	Safety Data Summaries
Section 14.3.1	Displays of Adverse Events
Table 14.3.1.1	Overall Summary of Treatment-Emergent Adverse Events (Safety Population)
Table 14.3.1.2	Summary of TEAEs by System Organ Class and Preferred Term (Safety Population)
Table 14.3.1.3	Summary of Treatment-Related TEAEs by System Organ Class and Preferred Term (Safety Population)

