Listing 16.2.4.2	Eligibility Criteria Satisfaction (All Enrolled Population)
Listing 16.2.4.3	Consent Information (All Enrolled Population)
Listing 16.2.4.4	Medical History (Safety Population)
Listing 16.2.4.5	Prior and Concomitant Medications (Safety Population)
Listing 16.2.4.6	Concomitant Procedures (Safety Population)
Section 16.2.5	Compliance and/or Drug Concentration Data
Listing 16.2.5.1	Study Drug Dosing Record (Safety Population)
Listing 16.2.5.2	Individual Plasma JBPOS0101 Concentrations (PK Population)
Listing 16.2.5.3	Individual Urine JBPOS0101 Concentrations (PK Population)
Figure 16.2.5.1	Individual Plasma JBPOS0101 Concentrations vs Time for Day 1 (PK Population) (For each subject, present the individual concentration in linear and semi-log scale.)
Figure 16.2.5.2	Individual Plasma JBPOS0101 Concentrations vs Time for Day 21 (PK Population) (For each subject, present the individual concentration in linear and semi-log scale.)
Section 16.2.6	Individual Pharmacokinetic and Efficacy Response Data
Listing 16.2.6.1	EEG Responses (EAS Population)
Listing 16.2.6.2	Seizure Diary Responses (EAS Population)
Listing 16.2.6.3	CGI-C Assessment Results (EAS Population)

---

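### The planned efficacy outputs cover only children treated for at least 26 days with a Day 28 EEG, and no all-dosed response rate is shown beside them

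*SAP*

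**What the plan says.** SAP 7.4 admits to the EAS only patients "who were treated with the investigational product for at least 26 days and completed the Day 28" overnight video-EEG and who have no major deviation bearing on efficacy. SAP 3.8.7 counts a missing, incomplete or unreadable Day 28 EEG as such a deviation. Protocol 7.5 gives the same definition and adds: "The EAS will be used for all efficacy assessments". The mEAS returns only patients whose deviations are attributed to COVID-19, and it is dropped if it coincides with the EAS. SAP 7.2 states: "Missing data will not be imputed".

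The output index in SAP section 8 follows these rules. Every EEG, time-to-relapse, diary and CGI-C table (14.2.1.1 to 14.2.4.2) is titled for the EAS or mEAS. The three efficacy listings (16.2.6.1 to 16.2.6.3) are titled for the EAS alone. The all-dosed set exists as the Safety Population but is assigned to safety.

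Other passages matter here:

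- SAP 7.1 promises that "All results collected in the database will be presented in listings".
- SAP 7.5 reports the numbers dosed and the numbers in each population.
- Protocol 4.2.2 says that, for a patient who leaves early, the investigator's "assessment of efficacy and tolerability of the investigational product will be recorded on Visit 6".

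**The concern.** Entry to the EAS depends on what happens after the first dose, and some of those events are likely to be linked to outcome. Protocol 4.2.1 lists serious or intolerable adverse events and risk to the patient's welfare among the reasons for withdrawal. Protocol 6.1.5.2 gives a doubling of seizure frequency over 7 days or more as an example of a serious event. A child withdrawn for worsening spasms would appear in the safety tables but in no titled efficacy table or listing.

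Such a child may still have efficacy data. The Schedule of Events places diary review and CGI-C at Days 7 and 21 and at the "Visit 6 / Early Termination Visit". Video-EEG is scheduled only at screening and Day 28, so for a child who stops early the diary and CGI-C are the only scheduled post-baseline efficacy measures.

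The study has one arm. The descriptive response rate is therefore the efficacy result, and Protocol 3.1.1 says the outcomes are meant to inform later studies. A completer rate read as the rate among treated patients could make those studies too optimistic.

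**Working it through.** **Inputs from the documents.** Enrolment closes once 35 patients have begun Treatment Period 1 (Protocol 4.2.3). The aim is at least 26 completers, with no replacement after dosing (Protocol 7.4, SAP 7.13).

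**The plan's own figures.** They imply non-completion of 1 − 26/35 = 25.7%, or 9 patients. No dropout rate is visible. An allowance of 25% would give 26/0.75 = 34.7, rounded up to 35, which agrees; 20% would give 33 and 30% would give 38.

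**Assumptions.** The EAS size is not given, so 26 stands in for it. Responder counts are not given either; 8 is used for illustration. Let *q* be the response rate among the 9 excluded.

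**Formulas.** EAS rate = 8/26 = 30.8% (exact 95% CI 14.3 to 51.8). All-dosed rate = (8 + 9*q*)/35. The two agree when *q* = 8/26.

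| *q* among the 9 excluded | All-dosed rate | EAS rate ÷ all-dosed rate |
|---|---|---|
| 0% | 8/35 = 22.9% (exact 95% CI 10.4 to 40.1) | 1.35 |
| 10% | 8.9/35 = 25.4% | 1.21 |
| 25% | 10.25/35 = 29.3% | 1.05 |
| 30.8% | 30.8% | 1.00 |
| 50% | 12.5/35 = 35.7% | 0.86 |

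In whole patients, 1, 2 or 3 responders among the 9 give 25.7%, 28.6% or 31.4%. The EAS rate is too high with 2 or fewer and too low with 3 or more.

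**Sensitivity to EAS size.** When no excluded patient responds, the ratio is 35 divided by the EAS size: 35/26 = 1.35, 35/28 = 1.25, 35/30 = 1.17, 35/32 = 1.09.

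**Sensitivity to the responder count** (26 in the EAS, none of the 9 responding; exact 95% CIs):

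| Responders | EAS rate | All-dosed rate | Gap (points) |
|---|---|---|---|
| 2 | 7.7% (0.9 to 25.1) | 5.7% (0.7 to 19.2) | 2.0 |
| 5 | 19.2% (6.6 to 39.4) | 14.3% (4.8 to 30.3) | 4.9 |
| 8 | 30.8% (14.3 to 51.8) | 22.9% (10.4 to 40.1) | 7.9 |
| 13 | 50.0% (29.9 to 70.1) | 37.1% (21.5 to 55.1) | 12.9 |

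**Removing EEGs missing for unrelated reasons.** If 2 of the 9 missed the EEG because of COVID-19 (assumed), the rate is 8/33 = 24.2% (11.1 to 42.3).

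**The case against.** The strongest reply is about weight. Efficacy is exploratory, no significance test is planned, and the primary safety analysis already uses every dosed patient. Protocol and SAP agree on the EAS. With the last escalation on Day 15, a set requiring about four weeks of treatment and the only on-treatment EEG answers a sensible early-phase question. All of this stands. It argues for keeping the EAS, not for showing it alone.

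An all-dosed EEG table would also add little new data. It mostly changes the denominator, and SAP 7.5 lets a reader rebuild the rate by hand. That is true for EEG. It is not true for the diary and CGI-C values of excluded children, which appear in no titled efficacy output.

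The index may be incomplete. SAP 7.3 promises efficacy subgroup summaries that have no titled table, SAP 7.1 promises listings of all results, and much of SAP 7.10.1, including its censoring table, is redacted. A hidden rule cannot be excluded. Even so, the readable population rules and titles all point the same way, and EAS-only listings sit badly with SAP 7.1.

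Finally, the size is assumed. The 9% response to nonstandard therapies in Protocol 1.2 comes from new-onset patients. Near that level the gap is about 2 points, and the intervals overlap widely in every case shown. This limits the claim about size but not the direction expected for early failures.

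**Conclusion.** The concern holds. On the visible text, EAS membership depends on post-baseline events, all titled efficacy outputs use the EAS or mEAS, and no response rate is planned on the all-dosed denominator. The EAS rate overstates response whenever excluded patients respond less often than those retained. That is the expected case for early failures, but it need not hold for loss to follow-up or withdrawal of consent.

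The ratio of 1.35 is the zero-response illustration at the plan's completer floor. It shrinks as the EAS grows or as excluded patients respond, and it can fall below 1. Completers are only a proxy for the EAS, and response definitions are redacted. The point affects how the efficacy estimate is read and leaves the primary objective untouched. The sponsor should correct it before database lock.

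**What to change.** Keep the EAS and mEAS as defined, label the EAS a completer analysis, and add the following to the SAP:

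1. **EEG response in the Safety Population**, with an exact 95% CI, beside the EAS result. Patients without an evaluable Day 28 EEG count as non-responders; those excluded for another deviation but with a readable EEG count as observed.
2. **A sensitivity version** that leaves out of the denominator patients whose EEG is missing for reasons unrelated to treatment, such as COVID-19. The rule for attributing reasons should be written down before database lock, because the trial is open-label.
3. **Diary and CGI-C summaries and listings** for all dosed patients with any post-baseline value, showing the number contributing at each visit. These remain available-case summaries and should be described as such.
4. **An entry in SAP section 4**, which now records no changes.

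The cost is SAP text and a few tables and listings from data already collected. Protocol section 7 allows further analyses to be placed in the SAP. Counting every missing EEG as non-response is conservative and can understate the true rate, so it should not stand alone. The reported rate may look less favourable.

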## **7.5 Subject Accountability**

Summaries of analysis populations and subject disposition will be presented by overall treatment (JBPOS0101) and will contain the following information:

- Number of subjects enrolled
- Number and percent of subjects with screen failure
- Number and percent of subjects with screen failure reason
- Number and percent of subjects who were dosed
- Number and percent of subjects who completed the study
- Number and percent of subjects who discontinued early and reason for early discontinuation
- Number and percent of subjects in the Safety, EAS, mEAS and PK Populations.

This summary will be based on the All Enrolled Population.

Subject disposition data, exclusions from the analysis populations, eligibility criteria satisfaction and consent information will be presented in listings.

## **7.6 Protocol Deviation Reporting**

Major protocol deviations will be identified prior to database lock and may include, but are not limited to, significant violations of inclusion/exclusion criteria, noncompliance with trial treatment taken, conditions such as vomiting and diarrhea or use of prohibited medications, and not following clinical trial protocol procedures.

All Protocol deviations will be listed.

## **7.7 Subject Demographics and Baseline Characteristics**

Subject demographic data and baseline characteristics will be summarized using descriptive statistics by overall treatment and will include the following parameters: sex, age, race, ethnicity, concomitant anti-epileptic drugs, height, weight, and body mass index (BMI). Demographic data and baseline characteristics will also be listed for safety population.

## **7.8 Medical and Surgical History**

Medical and surgical history will be coded using the Medical Dictionary for Regulatory Activities (MedDRA, Version 22.0 or later) and listed.

Medical history will be listed and summarized for safety population by System Organ Class (SOC) and Preferred Term (PT) for overall treatment.

## 7.9 Extent of Exposure

Exposure data will be presented in a listing and summarized by overall treatment.

Total exposure [mg] of a patient will be defined as the cumulative dose of study drug that a patient received during the course of the study. The extent (duration) of exposure will be derived in days as Date of last dose – Date of first dose + 1.

## 7.10 Analysis of Exploratory Efficacy Data

Exploratory Efficacy endpoints will be listed and summarized for following parameters: EEG, Seizure Diary and CGI-C.

The same efficacy analyses as in the EAS will also be performed for the mEAS population. If both populations coincide (i.e., there are no major protocol violations attributable to COVID-19 which affect the efficacy endpoint analysis) only the analyses in the EAS will be performed.

### 7.10.1 EEG

Situations	Date of censoring/event
[REDACTED]	[REDACTED]
[REDACTED]	[REDACTED]

A horizontal bar chart consisting of 20 solid black bars. The bars are arranged in a descending order of length from top to bottom. The lengths of the bars vary significantly, with some being very long and others very short. The chart is set against a white background and has no axes or labels.

[REDACTED]  
[REDACTED]  
In addition, the overall result of the video EGG at Day 28 (Visit 5 [ $\pm$  2 days]) will be summarized for overall treatment.

